2.4 Randomization and Blinding

The enrolled subjects will be randomized to treatment arm and control arm with 1:1 ratio. To avoid the selection bias caused by study team, the randomization will be done automatically by the Electronic Data Capture (EDC) system.

Randomization will occur after verifying an arterial line that is placed during the study procedure. A block randomization scheme with alternating block sizes of 4 and 6 subjects will be generated by study subject enrolled at each study site. No other stratification factors will be considered in randomization. By the random number generated for each subject within the randomization block, the web-based program will produce a cutoff value to ensure equal allocation between the treatment and control arms. The randomization code for each subject will be maintained by the study coordinator at the study site. The treatment allocation will be unblinded once the surgery operation starts.

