- Monitoring Phase: HPI 50 – 85 → evaluate flow / vascular tone indices and fluid responsive state.

Figure 1 : Treatment Protocol for Subjects Enrolled in the Treatment Arm

HPI Pressure & Flow Optimization Protocol

Note: Clinicians should validate the appropriateness of protocol recommendations, and provide treatment based upon their clinical judgment.

THIS DOCUMENT CONTAINS CONFIDENTIAL AND PROPRIETARY INFORMATION OF EDWARDS LIFESCIENCES, LLC. IT MAY NOT BE REPRODUCED OR DISCLOSED WITHOUT PRIOR WRITTEN PERMISSION FROM EDWARDS LIFESCIENCES, LLC.

Edwards Lifesciences, Edwards, the stylized E logo, HemoSphere, Acumen, Acumen IQ, FloTrac, and ForeSight Elite oximetry Sensor are trademarks of Edwards Lifesciences Corporation.

Randomization and Blinding

The randomization for this Trial will be implemented using an Interactive Web Response Systems (IWRS). The Sponsor will be blinded to the randomization codes. Participants will be randomized to either the control or treatment arm at enrollment. Study investigators will be blinded up until the time of the surgery. The clinician(s) involved in the consenting of the patient will be blinded to the randomization assignment and will not be involved in the care of the Trial subject. Once the intent of arterial line placement is confirmed with the anesthesia team, before surgery (the day before or in the morning of surgery), the subject will be randomized to either the treatment or control arm. The arterial line will then be placed. Randomization will be allocated in 1:1 ratio, stratified by site.

[figure not shown]

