6. SCHEDULE OF EVENTS & PROCEDURES

Screening

The study staff will review the subject's medical history for eligibility. Once the potential eligibility has been determined, the study will be discussed with the subject and interest in study participation will be determined. Subjects who fulfill all eligibility criteria will be scheduled for surgery within 30 days of the screening visit.

Pre-Procedure

During the pre-procedure period the following data will be collected:

- Labs:
 - Creatinine
 - Troponin
 - NT-proBNP
- Survey
 - Surgical Risk Assessment (NSQIP)

DAY 1 (DAY OF SURGERY)

On the day of the surgery, clinicians will be asked to follow the recommended treatment protocol for subjects enrolled in the treatment arm to reduce the subject's susceptibility to hypotension, (defined as MAP < 65 mmHg for at least one (1) minute), with guidance for decision support from the Hypotension Prediction Index (HPI) Feature Software. There is no restriction on the type of general anesthesia with or without regional anesthesia administered during the surgery.

The subjects in the treatment arm who are undergoing the planned non-cardiac surgery will have a radial arterial catheter inserted for pressure monitoring. The catheter will be connected to an Acumen IQ sensor and to the HemoSphere advanced monitoring platform with the Hypotension Prediction Index (HPI) Feature Software. The ForeSight Elite oximetry sensors will also be placed on subject's forehead to collect tissue oximetry data for observational purposes.

The subjects enrolled in the control arm will have a radial arterial catheter inserted for pressure monitoring and will have ForeSight Elite oximetry sensors placed on their forehead. The catheter will be connected to a FloTrac sensor and to the HemoSphere advanced monitoring platform, however the clinician will not be able to visualize the HemoSphere advanced monitoring platform and will not have information from FloTrac and ForeSight sensors. The subjects will be treated per standard of care, which includes radial arterial catheter monitoring for blood pressure monitoring.

The study staff may access intraoperative care data from the electronic anesthesia information management system. A designated study staff will be present during the procedures to collect data live. At the completion of the surgery, the hemodynamic monitoring data will be downloaded from HemoSphere advanced monitoring platform.

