THIS DOCUMENT CONTAINS CONFIDENTIAL AND PROPRIETARY INFORMATION OF EDWARDS LIFESCIENCES, LLC. IT MAY NOT BE REPRODUCED OR DISCLOSED WITHOUT PRIOR WRITTEN PERMISSION FROM EDWARDS LIFESCIENCES, LLC.

Edwards Lifesciences, Edwards, the stylized E logo, HemoSphere, Acumen, Acumen IQ, FloTrac, and ForeSight Elite oximetry Sensor are trademarks of Edwards Lifesciences Corporation.

DAYS 2-4 (POD 1-3)

The following data will be collected post-operation at Days (POD) 1, 2 & 3:

- Post-Operative Day 1
 - Any fluid and vasoactive medications
 - Obtain post-operative complications
 - Labs: Troponin
 - Post-Op delirium assessment (4AT⁵ or 3D-CAM¹⁷)
- Post-Operative Day 2
 - Obtain post-operative complications
 - Record adverse events
 - Labs: Creatinine and Troponin
 - Post-Op delirium assessment (4AT or 3D-CAM)
- Post-Operative Day 3
 - Obtain post-operative complications
 - Record adverse events
 - Labs: Troponin
 - POMS survey post-operation
 - Post-Op delirium assessment (4AT or 3D-CAM)

If the subject is discharged prior to any of the above schedule of events, a telephone call is sufficient to collect the appropriate required data.

Discharge from the ICU / hospital

The following data will be collected at discharge from the ICU / hospital:

- Obtain post-operative complications
- Record adverse events
- Concomitant Medications: medication that was administered post-operation

30-Day Follow-up

The following data will be collected at 30 days post-procedure via telephone if the subject is no longer in the hospital:

- Obtain post-operative complications
- Record adverse events
- Mortality determination
- WHODAS 2.0 Survey

THIS DOCUMENT CONTAINS CONFIDENTIAL AND PROPRIETARY INFORMATION OF EDWARDS LIFESCIENCES, LLC. IT MAY NOT BE REPRODUCED OR DISCLOSED WITHOUT PRIOR WRITTEN PERMISSION FROM EDWARDS LIFESCIENCES, LLC.

Edwards Lifesciences, Edwards, the stylized E logo, HemoSphere, Acumen, Acumen IQ, FloTrac, and ForeSight Elite oximetry Sensor are trademarks of Edwards Lifesciences Corporation.

Schedule of Events (SoE)

Table 2: Schedule of Events

Trial Procedure / Exam	Subject Screening	Pre-Procedure	Procedure	Post-OP Day 1	Post-OP Day 2	Post-OP Day 3	Discharge	30-Day Follow Up (+14 Days)
Obtain Informed Consent	X							
Perform Inclusion / Exclusion Evaluation	X							
Obtain Medical History / Subject Demographics ¹	X							
Assign Subject ID	X							
Assign Trial Arm	X							
Enter Subject Data into Monitor ³			X					
Vital Signs			X					

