Monitoring Duration			X					
Data download from Monitor ³			X					
Obtain Fluid and Vasoactive Medication Administration Record ²			X	X				
Obtain post-operative complications, if applicable			X	X	X	X	X	X
Labs: Creatinine ⁴		X			X			
Labs: Troponin		X		X	X	X		
Labs: NT-proBNP		X						
POMS ⁵						X		
NSQIP Surgical Risk Assessment ⁵		X						
Post-Op delirium assessment (e.g., 4AT or 3D-CAM) ⁵				X	X	X		
WHODAS 2.0 ⁵								X
Complete eCRFs	X	X	X	X	X	X	X	X
Record Adverse Events, if applicable			X	X	X	X	X	X
Obtain ICU / Hospital discharge Information							X	X
Phone Contact 30-day follow up / Mortality Determination								X

¹ Medical History / Subject Demographics / Surgical and Clinician Demographics can be obtained prior to procedure, either at the screening visit or on the day of procedure.

² Can be collected via the hospital record system anytime on the day of procedure or thereafter.

³ To be conducted for subjects assigned to treatment arm

⁴ To be collected on post-op day 1, 2 or 3.

⁵ To be collected if data or subject is available.

THIS DOCUMENT CONTAINS CONFIDENTIAL AND PROPRIETARY INFORMATION OF EDWARDS LIFESCIENCES, LLC. IT MAY NOT BE REPRODUCED OR DISCLOSED WITHOUT PRIOR WRITTEN PERMISSION FROM EDWARDS LIFESCIENCES, LLC.

Edwards Lifesciences, Edwards, the stylized E logo, HemoSphere, Acumen, Acumen IQ, FloTrac, and ForeSight Elite oximetry Sensor are trademarks of Edwards Lifesciences Corporation.

Procedure

The HPI SMART-BP Trial will collect data from up to 1486 subjects at up to 20 study sites across the United States. Up to 60 subjects may be included as roll-ins and will be analyzed separately from the pivotal cohort. Subjects will be randomly assigned to the interventional or control arms. The maximum number of subjects enrolled at each site will not exceed 20% of the total study population.

A subject will be considered enrolled in the Trial once the subject has signed the informed consent, has been assigned a Trial ID, an arterial line with either a FloTrac sensor (control arm) or Acumen IQ sensor (treatment arm) has been connected. Subjects may be screened for eligibility and consented on the day of surgery.

Subject participation will include preoperative study eligibility screening and consent, planned surgical intervention, Post-Op Day 1-3, ICU, hospital discharge, and 30 days post-procedure. Discontinued subject data will be analyzed under intent-to-treat and data will be used for safety and performance analyses.

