4. ANALYSIS POPULATIONS

4.1 Modified Intent-to-treat (mITT)

Modified Intent-to-treat (mITT) is defined as the study subjects who were exposed to the study product and will therefore be included in the effectiveness and safety analysis datasets. All randomized study subjects who have satisfied the population criteria will be classified in the designated population and will only be included in analyses for which they have available data. The mITT population will also be used to present exploratory analyses by the randomized treatment arm. The safety population is defined as all randomized subjects who were exposed to the study product; thus, the safety population will therefore be identical to the mITT population if all randomized subjects are exposed to the study product. In this clinical study, the primary effectiveness endpoint is a composite measurement of MINS, AKI, and serious infection adverse events, mITT will be the target population in interim, and final effectiveness analysis. The Roll-in subjects designed for the training purpose to avoid a learning curve bias will be analyzed separately. The safety population will be used to present the safety summaries by actual treatment received.

 Edwards	Revision Date: May 11, 2022	Rev	A	For Use Only by Affiliates of Edwards Lifesciences	Page 9 of 19
	Title	Statistical Analysis Plan for HPI SMART-BP Trial			

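### Protocol and SAP disagree on whether randomisation comes before or after the arterial line, and the exposure-based primary set drops patients who are randomised but never connected

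*Combined protocol and SAP*

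**What the plan says.** **Timing.** SAP 2.4: "Randomization will occur after verifying an arterial line that is placed during the study procedure". SAP 2.2 likewise lists the line as placed and the subject as then randomised. Protocol section 4 (Randomization and Blinding) randomises once the anaesthesia team confirms that a line is intended: "before surgery (the day before or in the morning of surgery), the subject will be randomized". Its next sentence says the line is placed after that. Table 2 of the protocol puts "Assign Trial Arm" in the screening column. On the interval from screening to surgery, protocol section 6 says "Subjects who fulfill all eligibility criteria will be scheduled for surgery within 30 days of the screening visit", but also "Subjects may be screened for eligibility and consented on the day of surgery".

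**Enrolment.** Protocol section 4 also ties randomisation to enrolment. The protocol counts a subject as enrolled only when the sensor belonging to the assigned arm is connected (section 4, General Design; section 5, Enrolled Subjects). SAP 2.2 does not require the sensor.

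**Analysis set.** SAP 4.1: "Modified Intent-to-treat (mITT) is defined as the study subjects who were exposed to the study product". SAP 8.1 runs the primary test on pivotal mITT subjects only. The term study product is not defined, but SAP 4.6 describes non-exposure in terms of the FloTrac and Acumen IQ sensors. Protocol section 7 (Analysis Methods) instead computes the z-statistic on the complete case population, which SAP 4.4 reserves for sensitivity analysis. SAP section 10 declares no changes from the protocol's analyses.

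**The concern.** The earlier a patient is randomised, the more can happen before a sensor is connected: surgery may be cancelled, the line plan may change, or the arm-specific sensor may simply not be attached. An exposure-based primary set removes those patients after assignment. If the reasons depend on arm and on risk, the groups compared are no longer the groups that were randomised.

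Arm-dependent removal is conceivable because the two sensors differ by arm, are placed before the procedure starts (protocol section 4), and the site coordinator keeps the randomisation code (SAP 2.4). At stake is the validity of the primary comparison. Power is hardly affected.

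**Working it through.** **1. The timing statements side by side**

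| Source | When the arm is assigned | Relative to the line |
|---|---|---|
| Protocol section 4, Randomization and Blinding | Day before or morning of surgery, on confirmed intent | Before |
| SAP 2.2 and 2.4 | Once the line is in and verified | After |
| Protocol Table 2 | Screening column | Before |

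The firm conflict is between the first two rows. The third is softer, because screening may take place on the day of surgery.

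The protocol's link between randomisation and enrolment is circular: enrolment needs the arm-specific sensor connected, and choosing that sensor needs the arm to be known.

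**2. Where a randomised but unconnected patient goes**

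- Not enrolled under the protocol, because no sensor was connected (SAP 2.2 would count the patient as enrolled).
- Not a late screen failure, because those patients were never randomised (protocol section 5; SAP 4.6).
- Not in mITT if exposure means the sensor, and not expressly restored by the FAS, PP or CC sets (SAP 4.2 to 4.4).
- No stated 30-day follow-up: the aborted-procedure rule applies only after connection to trial devices (protocol section 5, Early Withdrawal).

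Some gap between assignment and connection exists under every version. The SAP timing makes it shortest.

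**3. Illustration of size**

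The documents give no expected number of unconnected patients, so the loss and the risk of those lost are assumptions.

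Inputs from the documents: control rate 0.31; 1426 pivotal subjects at 1:1, so 1426/2 = 713 per arm; final boundary −2.01404 with one-sided p 0.02200 (SAP 2.3); unpooled standard error (SAP 8.1).

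Assumptions: no true effect, so both arms have rate 0.31; a fraction L is lost from the treatment arm only, with event rate q; a single look at the final boundary.

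- Remaining rate: r = (0.31 − L·q)/(1 − L)
- SE = √[0.31·0.69/713 + r(1 − r)/(713(1 − L))]
- One-sided error = Φ[(0.31 − r)/SE − 2.01404]

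For L = 3% (about 21 of 713) and q = 45%:

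- r = (0.31 − 0.0135)/0.97 = 0.3057
- SE = 0.0246
- shift = 0.0043/0.0246 = 0.176
- error = Φ(−1.838) = 0.033

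| Loss, treatment arm only | q = 31% | q = 45% | q = 60% |
|---|---|---|---|
| 1% | 0.022 | 0.025 | 0.029 |
| 3% | 0.022 | 0.033 | 0.050 |
| 5% | 0.022 | 0.043 | 0.082 |

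The q = 31% column shows that loss unrelated to outcome leaves the error where it was. Under no true effect, equal losses with equal risk in both arms move both rates together and leave the difference at zero.

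**4. Power**

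For a fixed two-sided 0.05 comparison of 0.31 with 0.2325, a balanced 5% loss takes power at 713 per arm from 90.9% to 89.5%, a fall of 1.4 points.

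**The case against.** The strongest reply is that the group affected is probably small and evenly spread. Both arms receive a sensor, so exposure is not peculiar to treatment. The sensor forms part of the pressure-monitoring line, and planned arterial-line monitoring is an inclusion criterion, so leaving it off at discretion is unlikely. A patient given the other arm's sensor is still exposed and, on a plain reading, stays in mITT. Investigators are said to be blinded until surgery, and SAP 2.4 opens the allocation only when the operation starts. All of this stands, and it limits the likely size. It does not settle which randomisation time governs, nor does it give the unconnected patient a place in the analysis. The blinding statements are also hard to apply fully, since someone must connect an arm-specific sensor before the procedure.

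A reader might infer that the SAP breaks a general intent-to-treat promise. The documents do not support that. The protocol's wording is "Discontinued subject data will be analyzed under intent-to-treat", which concerns discontinued subjects. Under the protocol's own enrolment rule, a subject who discontinues after enrolment has already been connected and so remains in mITT. What is true is narrower: no all-randomised set is defined.

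A reader might also take the schedule table as a third firm contradiction, with assignment up to 30 days ahead. Thirty days is a maximum and same-day screening is allowed, so the table needs aligning but proves little by itself.

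Finally, cancelled patients have no index operation from which to count 30 postoperative days. It is reasonable to leave them out of the primary set, provided they are reported by arm.

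**Conclusion.** The point holds as an inconsistency with a consequence. The current protocol and SAP put randomisation on opposite sides of line placement, the protocol's enrolment definition is circular with respect to randomisation, and the SAP's primary set excludes patients after randomisation without following them. The protocol's choice of complete cases for the same test is a further unreconciled difference.

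Bias is possible and has not been demonstrated. It would need losses that differ by arm in number or risk, and no figure in the documents indicates that they would. The rise from 0.022 to about 0.033 rests on a 3% loss confined to the treatment arm, a 45% event rate in those lost, no true effect and a single look. With balanced or outcome-unrelated loss it disappears. Reading exposure as sensor connection is itself an inference, supported by SAP 4.6. The plan should be corrected because doing so is cheap. Nothing here shows that the trial's result would be wrong.

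**What to change.** - State one randomisation time in protocol section 4, protocol Table 2, SAP 2.2 and SAP 2.4: after the line is verified and immediately before the sensor is connected.
- Separate randomised from enrolled, so that enrolment no longer depends on a sensor that can be chosen only after assignment. Use one definition in both documents.
- Define the primary set as all randomised pivotal subjects in whom anaesthesia for the index surgery started, analysed as randomised whichever sensor, if any, was connected.
- Follow all of these subjects to day 30.
- Reconcile the complete case wording in protocol section 7 (Analysis Methods) with SAP 8.1.
- Report by arm the number randomised but not exposed, with reasons, including cancellations before anaesthesia.

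The cost is wording in the two documents, follow-up of a few unconnected subjects, and a slight dilution of the effect from including them.

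### Site-level blocks alternating between 4 and 6, with past allocations open and codes kept by the site coordinator, leave allocation concealment weaker than the protocol describes

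*Combined protocol and SAP*

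**What the plan says.** SAP 2.4 (Randomization and Blinding) sets the scheme: "A block randomization scheme with alternating block sizes of 4 and 6 subjects will be generated by study subject enrolled at each study site". Site is the only stratum: "No other stratification factors will be considered in randomization". On disclosure it says "The treatment allocation will be unblinded once the surgery operation starts", and on custody "The randomization code for each subject will be maintained by the study coordinator at the study site". The same section says that "the randomization will be done automatically by the Electronic Data Capture (EDC) system" and gives avoidance of selection bias by the study team as the reason.

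Protocol section 4 (Randomization and Blinding) names an interactive web-response system and gives no block sizes: "Randomization will be allocated in 1:1 ratio, stratified by site". Its safeguards are that "Study investigators will be blinded up until the time of the surgery", and that "The clinician(s) involved in the consenting of the patient will be blinded to the randomization assignment and will not be involved in the care" of that subject. A later paragraph of the section extends blinding until surgery to staff as well as investigators.

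The timing of randomization differs by place:
- Protocol section 4 puts it after the intent to place an arterial line is confirmed, on the day before or the morning of surgery, and before the line is placed.
- SAP 2.4 puts it after the line has been verified.
- The protocol's schedule of events marks arm assignment in the screening column.

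**The concern.** Allocation concealment protects a trial from selection before assignment. Here each site runs a single sequence, and each past assignment on it becomes visible once that subject's surgery starts. Blocks are small, and the natural reading of alternating is a regular 4-6-4-6 order. Anyone who follows the sequence can therefore sometimes work out the next arm and often guess it. Blinding the consenting clinician to the current subject's assignment does not prevent inference from earlier subjects.

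The custody sentence adds to this. A coordinator who keeps the codes sits badly with staff who are blinded until surgery, and neither document limits the coordinator to codes already released.

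At stake is who is approached, scheduled or put forward. Eligibility includes a discretionary exclusion for conditions, such as a surgeon's request, that rule out tight blood pressure control. Knowing a current subject's arm early matters as well: the primary analysis set (SAP 4.1) contains only subjects exposed to study product, so a subject dropped between randomization and sensor connection leaves the primary analysis.

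**Working it through.** The documents give no predictability figure, so there is none to reproduce.

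**Inputs.** Block sizes 4 and 6, alternating, one sequence per site (SAP 2.4). Allocation 1:1 (both documents). Up to 20 sites and a 20% cap per site (protocol section 6, Procedure). 1426 subjects excluding roll-ins (protocol section 7). The average site then has 1426/20 = 71 subjects, and the largest has 0.20 × 1426 = 285.

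**Assumption.** Subjects at a site are randomized one after another, and all earlier allocations there are known.

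**Certain assignments.** In a block of 2k, an assignment is certain once one arm has been used up. The expected number is 2k/(k+1).
- Block of 4 (k = 2): 4/3 = 1.33
- Block of 6 (k = 3): 6/4 = 1.50
- Per cycle of 10 subjects: 2.83, or 28.3%

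**Correct guesses.** The rule is to guess the arm that is behind at the site, and to toss a coin when the arms are level. Completed blocks are balanced, so this rule needs no block sizes. The expected number correct is k + 2^(2k−1)/C(2k,k) − 1/2.
- Block of 4: 2 + 8/6 − 0.5 = 2.83
- Block of 6: 3 + 32/20 − 0.5 = 4.10
- Per cycle of 10: 6.93, or 69.3%, against 50% by chance

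**Variants.** These were simulated with an observer who updates the probable block size and position after each assignment (4000 sites of 71 subjects, 1000 sites of 285):

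| Scheme and knowledge | Certain, 71 subjects | Certain, 285 subjects | Guessed right, 71 / 285 |
|---|---|---|---|
| Alternating, first block known | 28.0% | 28.4% | 69.0% / 69.2% |
| Alternating, first block unknown | 24.6% | 27.5% | 69.1% / 69.2% |
| Random order, sizes 4 and 6 known, order hidden | 5.6% | 5.4% | 69.0% / 69.3% |

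With the scheme known, an average site runs about 7 full cycles, so about 7 × 2.83 = 20 assignments could be known in advance.

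**Larger blocks.** The same formula gives 4 + 128/70 − 0.5 = 5.33 of 8 for a block of 8, and 5 + 512/252 − 0.5 = 6.53 of 10 for a block of 10. Together that is 11.86/18 = 65.9%. The guess rate falls, but slowly.

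**The case against.** The strongest reply has four parts.

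- **Custody.** A code for each subject may mean only a record of codes already issued. SAP 2.4 describes automatic assignment by a web-based program, and no forward list at the site is mentioned. Someone there must also know the current arm before surgery, because the two arms use different sensors, which are placed before the procedure starts. A reader might infer that the coordinator can see every future assignment; the documents do not say so. What stands is that they do not exclude it, and the sentence does not fit blinding of staff until surgery.
- **Knowledge of the scheme.** The 28% requires site staff to know or infer it. Block sizes appear only in the SAP, whose page header restricts use to the sponsor's affiliates, and the SAP does not spell out a strict 4-6-4-6 order. This is a real condition on the 28%. It does not touch the 69%.
- **Source of the 69%.** It comes from small site-level blocks with open past allocations, not from the alternation. A reader might infer that random block order would restore 50%; the table shows that it does not.
- **Timing and safeguards.** Randomization the day before surgery is allowed, so cases may overlap and earlier allocations may not all be known. Surgery may follow screening by up to 30 days, which makes prediction at first approach harder, although same-day consent is also allowed. Automatic assignment and the blinded consenting clinician are real safeguards. These points lower the risk, but none prevents inference from allocations already open.

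**Conclusion.** The weakness is real, and its size is conditional. With the block scheme known or inferred and all earlier allocations at the site known, about 28% of assignments are certain in advance. If the first block size is unknown, this is about 25% at an average site of 71 subjects. About 69% can be guessed correctly from past allocations alone. Both figures assume sequential cases and would fall with overlap. All assignments would be known only if the coordinator held future codes, which the text leaves open but does not state. It would go too far to say that assignments in general are predictable, or that anyone is shown to have access to a forward list. What is established is that SAP 2.4, followed as written, gives weaker concealment than the protocol describes, and that the documents conflict on who is blinded and when randomization takes place.

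**What to change.** 1. Replace the coordinator sentence in SAP 2.4. State that the list is held only in the central system (named the same way in both documents) and that a site receives only the current subject's assignment when it is released.
2. Replace alternating block sizes with randomly ordered sizes that are not disclosed to sites. With sizes of 4 and 6 this cuts certain assignments from about 28% to about 5.6%.
3. If the guess rate of about 69% is also to fall, use larger or more varied block sizes.
4. Reconcile SAP 2.4, protocol section 4 and the schedule of events on when randomization occurs, who learns the arm before surgery in order to connect the sensor, and who stays blinded until then.

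The cost is system configuration and a few sentences, with no burden on patients and no material loss of power. Larger blocks allow slightly more imbalance within a site: the arms can differ by at most half a block, so 5 subjects with a block of 10 against 3 with a block of 6.
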